## Exclusion criteria

1. Patients readmitted to the ICU of a participating study site >72 hours after ICU discharge and already included in the study ( $\geq 1$  measurement of energy expenditure performed during prior admission). If a patient is readmitted within  $\leq 72$  hours of ICU discharge this is considered as a continuation of the last ICU admission for the purposes of this study.
2. Burns  $>20\%$  of body surface area.
3. Pregnancy.

## Intervention/exposure

Study subjects will be followed until ICU discharge or death, whichever occurs first.

All participating centers are encouraged to modify local nutrition protocols to recommend that:

- Indirect calorimetry is performed under standardized conditions (Appendix 1).
- Indirect calorimetry is performed within 3 days of ICU admission.
- Indirect calorimetry is repeated every 3-4 days until ICU discharge, death or in the event of limitations in treatment to best supportive care.
- Oxygen consumption ( $VO_2$ ), carbon dioxide production ( $VCO_2$ ), RQ and resting energy expenditure (REE) are documented in the patient's medical records.

Interpretation of investigations and energy prescriptions are left to the discretion of the attending physician or dietitian and are not regulated by the study protocol in any way.

## Outcomes

Primary:

- Change in REE (kcal/kg adjusted body weight\*/24 hours) over time in patients who stay in ICU for  $>10$  days.

\*Adjusted body weight is calculated as Ideal Body Weight (length in cm - 100) +  $\frac{1}{3}^*$ (Admission Body Weight - Ideal Body Weight). If admission body weight is less than ideal body weight, this value is used instead of adjusted body weight.

Secondary:

- Change in RQ over time in patients who stay in ICU for  $>10$  days.

- Change in REE and RQ over time in patients who stay in ICU for ≤10 days.

Exploratory:

Correlations between metabolic rate and CRP, albumin, urea/creatinine ratio, degree of organ failures (SOFA), ICU mortality, age and gender will be analyzed for hypothesis-generating purposes.

## Data collection

Pseudonymized patient data is reported from participating study sites through a secure online platform (Redcap™) on 1) admission, 2) on the day of each indirect calorimetry, and 3) on ICU discharge or death.

Participating centers are responsible for creating and maintaining a secure code key linking the study number attributed to a patient with a patient ID, to be stored in a secure location at the study site.

On admission:

- Admission date
- Admission diagnosis (ICD-10)
- Surgery prior to admission (YES/NO), elective or emergent
- ICU source of admission (Emergency department, ward, operating theatre, other ICU).
  - If ward or operating theatre → days in hospital before ICU admission.
  - If other ICU → days in previous ICU before admission.
- Outcome prediction score (SAPS 3, APACHE III/IV, MPM, etc.) and risk of death on admission (%)
- Demographic and anthropometric data:
  - Sex (male/female)
  - Age (years)
  - Actual body weight (kg)
  - Height (cm)
- Chronic comorbidities registered in electronic health records (YES/NO):
  - Hypertension
  - Ischemic heart disease
  - Heart failure

- Diabetes mellitus
- COPD
- Chronic kidney disease
- End-stage renal disease
- Liver cirrhosis
- Active cancer (not in complete remission)
- Haematological malignancy
- Solid organ transplant

On the day of each indirect calorimetry:

- REE (kcal/24 h), RQ,  $\text{VO}_2$  (ml/min),  $\text{VCO}_2$  (ml/min) and date of investigation
- Invasive mechanical ventilation (YES/NO) or renal replacement therapy (YES/NO)
- If YES to invasive mechanical ventilation:
  - fraction of inspired oxygen
  - positive end-expiratory pressure (cm  $\text{H}_2\text{O}$ )
- Sequential organ failure assessment (SOFA) score
- Fever ( $\geq 38.5^\circ\text{C}$ ) within 2 hours of measurement (YES/NO/MISSING)
- Results of daily blood tests if available from routine testing:
  - P-CRP (mg/L)
  - P-albumin (g/L)
  - P-urea (mmol/L)
  - P-creatinine ( $\mu\text{mol/L}$ )
  - Haemoglobin (g/L)
- Infusions of vasoactive medications (YES/NO, if YES → name of medication(s))
- Infusions of sedatives or analgesics (YES/NO, if YES → name of medication(s), if propofol → infusion rate at time of measurement)
- Infusions of parenteral and/or enteral nutrition (YES/NO, if YES → formulation and rate at time of measurement)
- Richmond Agitation-Sedation Scale (RASS) score on day of measurement

On discharge:

- Discharge date
- Survival status (ALIVE/DEAD)
- Sepsis during ICU stay (YES/NO, if yes → septic shock or sepsis)

On completion of enrollment at an individual study site:

- Total number of patients admitted during the study period.

## Sample size considerations

The goal of this study is to include  $\geq 200$  patients with an ICU length of stay of  $>10$  days. Based on data from the Swedish Intensive Care Registry between 2015-2019, these patients accounted for 5% of all ICU admissions [9]. This proportion is comparable to results from a registry study conducted in Australia and New Zealand of over one million ICU admissions [8]. Based on these figures we intend to screen 6000 unique patients for study participation, accounting for the possibility that multiple measurements of indirect calorimetry are not consistently performed. Based on Swedish registry data approximately 1250 unique patients with at least one measurement of indirect calorimetry will be included in the analysis.

## Statistics

Descriptive data will be presented as mean  $\pm$  standard deviation or median (interquartile range) as appropriate. The primary and secondary outcome measures will be analysed using a generalized linear mixed-effects model. Exploratory outcomes will be analysed using generalized linear regression models. If values are found to be not missing at random, conditional logistic regression censoring will be used to calculate inverse probability weights for accounting for difference in drop-out probabilities. The predetermined level of statistical significance is set to  $\leq 0.05$ .

A detailed statistical analysis plan will be published before the database is locked and analysis begins.

## Ethics

The study has received approval from the Swedish Ethical Review Authority (Dnr 2021-02750) and has been granted a waiver of informed consent. Approval from ethical review boards at study sites outside of Sweden must be granted before enrollment can begin. Due to the observational nature of the study and pseudonymized reporting of routinely collected data, we recommend an application for a waiver of informed consent, or if this is not granted, the possibility for delayed consent from patients or next of kin if applicable.

## Statistical analysis plan (updated 2025-04-08)

For descriptive statistics, continuous variables will be presented as means  $\pm$  standard deviations (SD) or median [interquartile range (IQR)], as appropriate. Distributions will be visually inspected using histograms and assessed for normality using quantile-quantile plots.

Generalised linear mixed regression models will be used to study the association between primary (REE) as well as secondary outcomes (RQ,  $\text{VO}_2$ ,  $\text{VCO}_2$ ) and explanatory variables of interest. Explanatory variables will include a group of potentially relevant variables (days in ICU on measurement, age  $>/<$  60 years, sex, airway pressure (PEEP),  $\text{FiO}_2$ , vasopressor therapy (yes/no), fever (body temperature  $\geq 38.5^\circ\text{C}$  at time of measurement), calories administered at time of measurement, Richmond Agitation-Sedation Scale (RASS), degree of inflammation (plasma CRP), renal replacement therapy (yes/no), body weight, diagnostic group (medical, surgical, presence/absence of sepsis)). Further variable selection will be conducted in a data-driven way, either backward or forward selection, as appropriate. For each outcome, the link function and model family will be chosen based on the visual inspection of their distribution and model fit diagnostics such as residual plots. Patient and study site will be included as random effects allowing for a random intercept for each. Random slopes over time will be included in the model if their respective estimated coefficients are statistically significant and if the model fit in terms of Akaike's information criterion (AIC) is improved compared to the random intercept model. Possible correlations between the random effects will be modelled using an unstructured covariance matrix unless the AIC suggests a different covariance structure for best describing the random variation in the data. Any additional explanatory variables will be treated as fixed effects. For each additional explanatory variable, we will investigate two research questions. First, we want to explore possible associations with each outcome variable. Second, we want to study how well the explanatory variables taken together explain the variation in each outcome variable. The best final adjusted models will be selected based on the AIC. Results will be reported as (exponentiated) regression coefficients and 95% confidence intervals. If a non-linear relationship between any outcome and any explanatory variable is suspected, using restricted cubic splines will be explored.

---

 Classified as Sepsis-3 och primary diagnosis of sepsis. Sepsis-3 coding is not available in the Australian cohort. A sensitivity analysis including or excluding the primary diagnosis of sepsis will be performed.

Frequencies and patterns of missing data will be investigated for each outcome and explanatory variable by studying summary tables and plots. If missing at random can be assumed and frequencies are below 3% at each time point, this missingness will be ignored, and observations dropped. Explanatory variables with more than 30% missing values at baseline will not be considered, except for the SOFA score, which is not available in the Australian subpopulation. SOFA score will be investigated in non-Australian patients only. As an exploratory analysis, the SOFA score will be imputed in the Australian cohort. Multiple imputation will also be investigated for explanatory variables between 3 and 30% missing values at baseline. If missing at random cannot be assumed, alternative modelling approaches will be considered. Conditional logistic regression will be used to calculate the inverse probability of censoring weights to control for selective drop-out in patients discharged alive from the ICU.

For hypothesis-generating purposes, longitudinal K-means clustering or clustering with dynamic time warping will be used to investigate potential subpopulation phenotypes based on transitions in energy expenditure over time, as appropriate.

All analyses will be performed in R version 4.4.0 or later. The predetermined level of statistical significance for the primary outcome is set to  $\leq 0.05$ . For all other outcomes, no adjustments for multiple comparisons will be made due to the explorative nature of this part of the study. Hypotheses will be generated for target populations with similar characteristics as our sample population, leaving external validity investigations to future confirmatory studies.

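### Age is collected in years but enters the SAP models as an unexplained split at 60; if its effect is roughly linear, about a quarter to a half of the age information is lost.

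*Combined protocol and SAP*

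**What the plan says.** - **Protocol, Data collection:** age is recorded in years at admission. Fever is recorded as a category, "within 2 hours of measurement (YES/NO/MISSING".
- **Protocol, Outcomes:** age is an exploratory correlate of metabolic rate with no cut-point: "ICU mortality, age and gender will be analyzed for hypothesis-generating purposes".
- **Protocol, Statistics:** "Exploratory outcomes will be analysed using generalized linear regression models", again with no cut-point.
- **SAP (updated 2025-04-08):** the candidate covariates include "age $>/<$ 60 years, sex, airway pressure (PEEP" and so on. PEEP, FiO2, RASS, CRP and body weight carry no cut. No reason is given for 60 or for a binary form.
- **SAP, selection:** "Further variable selection will be conducted in a data-driven way, either backward or forward selection, as appropriate".
- **SAP, aims for the covariates:** the first is the association of each with each outcome. The other is given as "Second, we want to study how well the explanatory variables taken together explain the variation in each outcome variable".
- **SAP, non-linearity:** where it is suspected, "using restricted cubic splines will be explored".

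**The concern.** Age is the only covariate in the SAP list that is collected as a number and then cut in two. Fever, vasopressor use and renal replacement are yes/no items by nature or by collection. A split treats patients of 61 and 85 as alike, and patients of 59 and 61 as different. Unless the true effect is a step at 60, this discards information already in the database.

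The SAP's two covariate aims are both touched: the age association is estimated less precisely, and the explained variation comes out too low. Patient-level covariates correlated with age are left partly confounded by it. A weakened age term is also more likely to be dropped by data-driven selection, and then no age adjustment remains.

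The spline provision does not repair this. It applies only when non-linearity is suspected, and a spline cannot be fitted to a two-level variable.

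**Working it through.** The documents state no figure that depends on how age is coded, so there is none to reproduce. The check asks how much of a linear age effect the split retains.

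**Inputs.** From the documents: age in years, adults only, split at 60, and "approximately 1250 unique patients with at least one measurement of indirect calorimetry will be included in the analysis". Assumed, because the documents do not give them: the age distribution, a linear age effect, and the correlations used below.

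**Information kept.** This is k = r² between age and the indicator for age above 60.

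- Normal age: k = φ(c)² / [p(1−p)], where c = (60 − mean)/SD and p = P(age > 60).
  - Mean 60, SD 15: c = 0, p = 0.5, so k = 0.3989²/0.25 = 0.637, a loss of 36%.
  - Mean 70, SD 12: c = −0.833, p = 0.798, so k = 0.2819²/(0.798 × 0.202) = 0.492, a loss of 51%.
- Uniform age: k = 3p(1−p).
  - Range 18–90: p = 30/72 = 0.417, so k = 0.729, a loss of 27%.
  - Range 25–90: p = 30/65 = 0.462, so k = 0.746, a loss of 25%.
- Other shapes, by simulation:

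| Assumed age distribution | Loss (1 − k) |
|---|---|
| Normal truncated to 18–95 (60/15, 65/14, 60/18) | 33–37% |
| Left-skewed (scaled beta, 18–92) | 29–35% |
| Two-peaked (35% around 38, 65% around 69) | 27% |

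The loss passes one half only when 60 lies more than about 0.8 SD from the mean. At mean 70, SD 10 it is 56%.

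**Equivalent sample size.** With independent patients and k = 0.637, 1250 × 0.637 = 796: the split gives about the precision on the age slope that 796 patients would give with age in years.

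**Explained variation.** For age alone the split captures k, or 49–75% of what linear age would. If age explained 10% of between-patient variance, the split would show 4.9–7.5%. The SAP's aim concerns all covariates jointly, where the proportional loss is smaller. Suppose age explains 10% and an uncorrelated covariate 20%. The split then keeps (10 × 0.637 + 20)/30 = 88% of the joint figure for normal 60/15, and (10 × 0.492 + 20)/30 = 83% for normal 70/12. Letting the two covariates correlate up to 0.4 in either direction gave about 75–92%.

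**Residual confounding.** For a covariate with correlation ρ with age, the fraction of age confounding left after adjusting for the split is (1 − k)/(1 − kρ²).

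- k = 0.637: 0.363/0.975 = 37% at ρ = 0.2, and 0.363/0.898 = 40% at ρ = 0.4.
- Across k = 0.492 to 0.746 and ρ = 0.2 to 0.4: about 26–55%.

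**Power for the age association.** This uses the Fisher z approximation at patient level, two-sided 0.05, with r replaced by r√k. All rows have n = 1250.

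| True r | Age in years | Split (k from 0.492 to 0.746) |
|---|---|---|
| 0.04 | 29% | 17–23% |
| 0.08 | 81% | 51–69% |
| 0.12 | 99% | 85–96% |

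With 200 patients, r = 0.20 gives the same pattern as the 0.08 row.

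**The case against.** The strongest reply is that nothing confirmatory is affected. Age is essentially constant within a patient and the models carry a patient random intercept, so change in REE over time is not shown to suffer. The protocol calls the age correlation hypothesis-generating, and the SAP treats everything beyond the primary outcome as explorative. This stands, and it limits the weight of the point.

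Several objections to the size also stand:

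- The age distribution and the shape of the effect are assumed. The upper end of the range is not a bound, and the loss is nil for a true step at 60.
- The joint explained variation falls much less than the age-alone figure.
- The power loss is marked only at intermediate effect sizes.
- The residual confounding is a fraction of an unknown bias, which could be negligible in absolute terms.

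It can also be said that a cut-point fixed in advance prevents searching for one later, and that an analyst could go back to age in years to fit a spline. The first is true, but age in years needs no cut-point at all. The second is not written in the SAP and would not be triggered by a linear effect.

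**Conclusion.** The concern holds. The SAP replaces a variable collected in years with an unexplained split at 60, and nothing in the plan restores it. Under a roughly linear age effect and the age distributions tried here, about 25–51% of the age information is lost. Less precise age associations and understated explained variation follow, both against the SAP's stated covariate aims.

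The certain scope is the SAP mixed models in which age survives selection. Whether the split also governs the exploratory age correlation in the protocol is not stated. The textual finding is firm; its size rests on assumptions that the documents cannot narrow. No effect on the primary outcome or the sample size is claimed. The change is worth making because it is nearly free, not because a main conclusion is at risk.

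**What to change.** In the SAP's covariate list, replace the split with age in years, entered linearly or as a restricted cubic spline with 3 or 4 knots, wherever age is a candidate or adjusting covariate. Report the effect per 10 years. State that the exploratory age correlation under Outcomes uses the same coding.

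If a split at 60 is kept, use it for descriptive display only and define the groups as <60 and ≥60. The present notation does not assign patients aged exactly 60, about 1.4–2.8% under the assumed distributions. If there is a reason for 60, the SAP should give it.

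Cost: one phrase in the SAP, 0–2 extra degrees of freedom, and no new data.

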## Background

Critical illness has profound effects on human metabolism. The most prominent feature in the early phase is an upregulation of catabolic pathways, which promotes the production of endogenous energy substrates and net protein breakdown [1].

Historically, it was assumed that intensive care unit (ICU) patients have an increased requirement of energy substrates [2, 3]. This belief was supported by small observational studies using indirect calorimetry [4, 5]. More recent studies have called this into question, finding that critically ill patients on average have a metabolic rate similar to that of healthy subjects [6]. Energy expenditure in the individual patient is highly variable and cannot be accurately estimated from population characteristics [7]. Metabolic rate may change over time, and is likely influenced by the underlying cause and trajectory of critical illness.

Energy expenditure is readily measured in the clinical setting by indirect calorimetry. This method has been available in intensive care for several decades. Despite this, there is very little published data describing trends of energy expenditure and substrate utilization in patients with

a prolonged ICU stay. While this group only constitutes a small fraction of ICU patients, it accounts for a large part of ICU resource allocation, morbidity and suffering [8]. Several studies have been conducted in recent years to better characterize patients with persistent critical illness, focusing on markers of catabolism and inflammation [9, 10]. It is not known if these changes are associated with alterations in energy metabolism and substrate utilization.

Bridging these knowledge gaps will improve our understanding of the nutritional needs and metabolism of patients beyond the early phase in ICU. A better characterization of the relevant physiology is an essential step towards improving patient outcomes. We therefore plan to conduct an observational multicenter study to address these questions.

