## Hypothesis

There is a significant change in mean energy expenditure and respiratory quotient (RQ) between the early (day 1-3), intermediate (day 4-10) and late (>10 days) phase in ICU.

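### The only intake term in the RQ model is calories, which cannot separate fat from carbohydrate, so the adjusted time effect can reflect drift in the infused mix

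*Combined protocol and SAP*

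**What the plan says.** **RQ as an objective.** The protocol's Outcomes section lists as secondary "Change in RQ over time in patients who stay in ICU for" more than 10 days, and also the RQ course in patients with shorter stays. The Hypothesis section expects both energy expenditure and RQ to differ between the early, intermediate and late phases. The Background describes the knowledge gap as the lack of data on "trends of energy expenditure and substrate utilization in patients with" a long stay.

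**What is recorded.** Under Data collection, each calorimetry day includes "Infusions of parenteral and/or enteral nutrition (YES/NO, if YES → formulation and rate at time of measurement" and, for sedation, "if propofol → infusion rate at time of measurement". Intravenous glucose and citrate are not listed.

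**What is modelled.** The SAP gives one list of candidate variables for all four calorimetry outcomes. Its only intake term is "calories administered at time of measurement". The SAP does not say whether propofol lipid counts towards those calories. It names no term for carbohydrate, fat, formulation or propofol. Further selection is data-driven, and AIC decides the final model.

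**Feeding.** Under Intervention/exposure, "energy prescriptions are left to the discretion of the attending physician or dietitian", so nothing in the study holds the infused mix constant over the stay.

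**The concern.** RQ depends on the mix of substrates oxidised: close to 1.0 for carbohydrate and 0.7 for fat. Two measurements with the same calories, one mostly fat and one mostly carbohydrate, look the same to the planned model but push RQ in opposite directions. If the mix changes systematically with ICU day, for example because a lipid-based sedative is withdrawn while feed is increased, the coefficient for days in ICU takes up that change.

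The interpretation of the adjusted RQ result is at stake. A calorie term suggests that feeding has been accounted for. A reader would then take the remaining time effect as a change in metabolism at given intake, when part of it may be a change in what was infused.

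**Working it through.** The documents give no RQ effect size, standard deviation or intake composition, so there is no figure of the plan's own to reproduce. The check compares recorded with modelled variables, then sizes the effect under stated assumptions.

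**1. Recorded against modelled.** Formulation × feed rate gives carbohydrate, fat and protein per hour once formulations are linked to product composition. Propofol rate × lipid content adds fat. None of these appears in the SAP's list. The other listed variables (FiO2, PEEP, fever, RASS, CRP and so on) do not measure substrate supply.

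**2. Algebra.** From stoichiometry, RQ is 6/6 = 1.00 for glucose and 16/23 = 0.696 for palmitate. Ignoring protein and holding calories fixed:

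RQ shift ≈ (fraction of oxidised energy that comes from intake) × (fall in fat share of intake) × (1.00 − 0.696)

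| Fraction from intake | Fall of 5 points | 10 points | 15 points | 20 points |
|---|---|---|---|---|
| 0.25 | 0.0038 | 0.0076 | 0.0114 | 0.0152 |
| 0.50 | 0.0076 | 0.0152 | 0.0228 | 0.0304 |
| 0.75 | 0.0114 | 0.0228 | 0.0342 | 0.0457 |

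**3. Precision.** Assume 200 paired patients (the protocol's long-stay target), an RQ SD of 0.10 and a within-patient correlation of 0.3. Only the 200 comes from the documents. SE of a change = 0.10 × √(2 × 0.7/200) = 0.0084. The table therefore runs from 0.0038/0.0084 ≈ 0.5 SE to 0.0457/0.0084 ≈ 5.4 SE.

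**4. A worked case with protein.** Assume quotients of 1.0, 0.7 and 0.8 for carbohydrate, fat and protein, feed with 50/30/20% of energy from each, and 1600 kcal/day at both times.
- Early, 400 kcal from propofol lipid plus 1200 kcal feed: the mix is 37.5/47.5/15%, and 0.375 × 1.0 + 0.475 × 0.7 + 0.15 × 0.8 = 0.8275.
- Late, feed only: 0.50 × 1.0 + 0.30 × 0.7 + 0.20 × 0.8 = 0.870. The difference is 0.0425 at identical calories.
- With 200 kcal from propofol early: the mix is 43.75/38.75/17.5%, the quotient is 0.8488 and the difference is 0.021. If only half of what is oxidised reflects intake, this becomes about 0.011, or 1.3 SE.

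**5. Simulation.** There were 200 patients with measurements on days 2, 5.5, 9, 12.5 and 16, and a random-intercept model with variance components treated as known. Endogenous RQ was constant at 0.80, between-patient SD 0.05 and residual SD 0.06. Mean calories doubled from day 2 to day 9 and then stayed level. Fat share started at 45% and fell linearly. Each scenario had 200 runs. There was no true change in endogenous substrate use. Entries are the estimated day 2 to 16 change, with the percentage of runs at p ≤ 0.05.

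| Intake share of oxidation at full feeding | Fall in fat share | Calories only | Carbohydrate and fat |
|---|---|---|---|
| 50% | 0 | 0.000 (3.5%) | 0.000 (2.5%) |
| 50% | 5 points | 0.006 (12.5%) | 0.000 (6%) |
| 50% | 10 points | 0.012 (40.5%) | −0.001 (7.5%) |
| 50% | 15 points | 0.019 (74%) | 0.000 (4.5%) |
| 75% | 0 | 0.000 (6%) | 0.000 (5%) |
| 75% | 5 points | 0.009 (29%) | 0.000 (7.5%) |
| 75% | 10 points | 0.019 (73.5%) | 0.000 (3%) |
| 75% | 15 points | 0.029 (97%) | 0.002 (4.5%) |

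Protein is ignored here, so calories plus fat is the same model as carbohydrate plus fat. With calories only, the time effect appears whenever the mix drifts. It disappears once composition is in the model.

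**The case against.** **Oxidising infused substrate is real substrate use.** A reader might infer that an RQ trend without composition terms is simply wrong. The documents do not support that. The stated aim is to describe longitudinal change, and nowhere do they promise to attribute the RQ course to illness independently of feeding. This objection stands: the unadjusted course answers a legitimate question.

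**Intake may lie on the path from ICU day to RQ.** Sedation and feeding follow the course of illness, so conditioning on them changes the quantity estimated. That is true, and it argues against making the composition model the only RQ analysis. It does not defend the present plan, which already conditions on intake through a variable that cannot distinguish fat from carbohydrate.

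**The size is uncertain.** A reader might take the 0.0425 case, about 5 SE, as typical. It needs a quarter of early intake to come from propofol lipid on average and all oxidation to mirror intake. Neither is in the documents, and small drifts give negligible shifts. RASS is on the SAP's list and may partly track the withdrawal of propofol, which the simulation did not include. Rising calories do not remove the effect, since calories rose in the simulation too.

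**The plan does not forbid macronutrient terms.** It allows additional explanatory variables and selection, but prespecifies none for composition, and selection could drop even calories.

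**Derived intake would be incomplete.** This stands, because intravenous glucose and citrate are not recorded. It is a limitation to state, not a reason to leave the recorded formulation and propofol rate unused.

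**Conclusion.** The point holds as a matter of covariate choice for a secondary outcome. The planned intake term cannot separate fat from carbohydrate, the recorded data largely can, and the adjusted RQ time effect is open to misreading if the infused mix drifts with ICU day. The possible shift is about 0.004 to 0.046 RQ units. That assumes intake supplies 25 to 75% of oxidised energy and that its fat share falls by 5 to 20 points. Against an assumed SE of 0.0084 this runs from negligible to several standard errors. Whether and how far the mix drifts in this cohort cannot be known from the documents.

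Two stronger readings are not supported. One is that the RQ analysis is invalid: the course without intake terms is a proper description, and the SAP treats everything beyond the primary outcome as explorative. The other is that the primary result is compromised: REE does not depend on the fat-to-carbohydrate mix in the way RQ does.

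**What to change.** In the SAP paragraph that lists the explanatory variables:

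1. Define calories administered as feed energy plus the energy of propofol lipid.
2. Prespecify for RQ a model that keeps calories and adds carbohydrate and fat intake, or their shares of energy, derived from the recorded formulation, feed rate and propofol rate. Exempt these terms from data-driven selection. Shares are undefined when nothing is infused, so amounts per hour, with zero for no infusion, are easier to handle. If protein is left out of the calorie total, calories plus one of the two terms suffices, because all three would be collinear.
3. Report the RQ time effect with and without these terms. Read the first as change at given intake and the second as overall change in substrate use.
4. State that intravenous glucose and citrate are not recorded, so derived intake is incomplete.

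The cost is a lookup table from formulation to macronutrient content, one or two degrees of freedom in the RQ model, and a possible loss of observations where the formulation is missing. The SAP should say how its 3% and 30% missing-data thresholds apply to the derived terms. No new data collection is needed.
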